Study setting and population:	KMP is a resource-limited, densely populated, high HIV disease burden area in Cape Town, where the use of health services among men is sub-optimal. Recruitment will be conducted by trained mobile clinic staff at high foot-traffic sites in the KMP community. Recruitment efforts will focus on young men in multiple mobile testing sites that are located in areas within KMP where there is a high burden of HIV.
Study size:	
In phase 1, approximately 20 men will be invited to participate in formative research through insight workshops for U=U message development. After the initial message development, about 20 more men will be invited to give feedback and suggest improvements to ensure understanding and acceptability of the messaging.
 
In phase 2, 40 clinic days will be randomized to intervention or control, with 100 men in the vicinity of the Tutu Tester receiving invitation cards for testing on each day (N=4,000).

Process:	In phase 1, mobile clinic staff will invite men to participate in an insight workshop at a community location. Men who agree to participate will respond to questions and take part in group brainstorming activities that will inform development of U=U messaging.

	
The research team will map the ideas and themes and use these to create an invitation to men. Their feedback will be used to calibrate the messages for the phase 2 trial.
 
In phase 2, a trained recruiter will deliver a U=U invitation message on intervention days and standard HIV testing messaging on control days to encourage HIV testing at a mobile clinic. On each day, recruiters will deliver about 100 invitation cards to young men in the vicinity of the mobile testing van where free HIV testing will be available.

Duration:	Phase 1 will run for one month. Phase 2 will run for 3 months.
Analysis:	In phase 1, acceptability will be measured through workshop feedback. In phase 2, a chi-squared test will estimate the effect of U=U messaging on HIV testing uptake compared with standard of care. We will also compare HIV positivity by study arm. Logistic regression analysis will model the effects of participant demographics, binary line of sight of mobile clinic, and time of day on testing uptake and time to presentation at the clinic.

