**2.4.a. Design** – In phase 1, we will develop a U=U message using a participatory, human-centered design framework. There is increasing recognition that intervention design should incorporate viewpoints from the target audience to enhance collaboration, improve acceptability, and increase uptake (Byrne & Sahay, 2007; Mabunda, Khoza, Van den Borne, & Lebese, 2016). Thus, this participatory research will include workshops of approximately 40 men from a population that may potentially be recipients of the intervention.

**2.4.b Process** – Mobile clinic staff will invite approximately 20 men from high traffic locations in the KMP region to participate in design workshops for the development of a U=U message, that even if HIV positive they can be untransmittable, to normalize HIV and mitigate the fears of testing HIV positive. Each workshop participant will be asked to give informed consent, and then a trained facilitator will present the U=U message to the participants and facilitate the group to develop a message that resonates with them in language that is sufficiently colloquial to enable easy understanding among local

men. Their suggestions and statements will be recorded in written form verbatim and used to generate the invitation message. Once developed, the message will be presented to approximately 5-10 more men from within the community who will be invited to rate and suggest improvements to the acceptability of the prototype message. Following this exercise, the message will be fine-tuned and the final message will be printed on invitation cards for the phase 2 randomized trial.

## 2.5. Phase 2

2.5.a. Design – In phase 2, a cluster randomized trial will be conducted to determine the effect of the U=U message on HIV testing uptake. Individual mobile clinic days (i.e., the tester being parked at one site for one day) will serve as the unit of randomization, with each site day being assigned to the treatment or control condition via a computer-generated randomization process. Randomization will be stratified by testing location so that an equal number of clinic days at each location within KMP are assigned to each study group. On each mobile clinic day during the study, men in the vicinity of the mobile clinic will be offered invitation cards for same-day testing. Invitation cards will have unique identification codes. The information content on the referral cards and the mobilization approach will vary depending on condition.

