time taken to get tested, age, whether the participant brought a peer or partner, whether the person stayed for an HIV test or not and HIV status. Several open-ended questions to learn about men's perceptions of the U=U messaging may also be asked including: if they had any previous understanding of U=U, what they think about the message and how this might change their behavior. The DTHF team will translate and validate the questionnaire and confirm its cultural appropriateness. As per standard operating procedure, those who test HIV positive will receive post-test counselling and assessment by a nurse and will be referred to their preferred clinic facility for HIV treatment.

2.5.f. Sample size and power calculations – In phase 2, the DTHF Tutu Tester will circulate between approximately four different locations within KMP. The Tutu Tester will be based in only one location on any given day. Clusters will comprise men who receive invitation cards on the same clinic day. Power calculations assumed 8 percent HIV testing uptake among men in the control group (based on two operational pilots conducted by our team) and an intraclass correlation of 0.02. With 40 clinic days in the study and 100 men within the vicinity of the Tutu Tester receiving invitation cards on each clinic day, we will have 80 percent power to detect a difference in HIV testing between groups of at least 5 percentage points.

2.5.g. Outcomes and analysis – The primary outcome will be HIV testing uptake, measured at the Tutu Tester based on presentation of the invitation cards. A chi-squared test will be conducted to estimate the effect of the intervention on HIV testing uptake. Logistic regression models will also be estimated to control for location, time of day, and distributor effects. Additional outcomes examined will include the proportion of males tested who are HIV-positive (and newly HIV positive).

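### The primary chi-squared test ignores the randomised clinic days; at the plan's own ICC its false-positive rate is about 25%, not 5%

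*Combined protocol and SAP*

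**What the plan says.** Section 2.5.a makes phase 2 a cluster randomised trial: "Individual mobile clinic days (i.e., the tester being parked at one site for one day) will serve as the unit of randomization". It also stratifies the allocation: "Randomization will be stratified by testing location so that an equal number of clinic days at each location within KMP" go to each arm. Section 2.5.f defines the clusters: "Clusters will comprise men who receive invitation cards on the same clinic day". The power calculation there assumes 8% uptake in controls, "an intraclass correlation of 0.02", 40 clinic days and 100 men per day. It claims 80% power for a difference of at least 5 percentage points.

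Section 2.5.g then names the primary analysis: "A chi-squared test will be conducted to estimate the effect of the intervention on HIV testing uptake". The Analysis row of the synopsis agrees: "In phase 2, a chi-squared test will estimate the effect of U=U messaging on HIV testing uptake compared with standard of care". The supporting analysis is: "Logistic regression models will also be estimated to control for location, time of day, and distributor effects". The synopsis gives a slightly different covariate list for the logistic model (demographics, line of sight, time of day). Neither section mentions a clinic-day term, cluster-robust variance, GEE, a mixed model, a cluster-adjusted chi-squared statistic or an analysis of day-level proportions, and nor does any other part of the document. No significance level is stated.

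**The concern.** The design and power sections treat the clinic day as the unit of randomisation and expect men approached on the same day to resemble each other. The primary test does neither. An ordinary chi-squared test on individual men takes its variance from 4,000 independent observations, whereas the arm comparison rests on 20 days against 20 days. It also makes no use of the location strata. The logistic model does adjust for location, but without a term or variance correction for the day it leaves out the same source of variation.

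The p-value for the primary outcome would therefore be too small, and any unadjusted interval too narrow. This matters for the decision, because section 5 says that U=U messaging should become part of a wider intervention package if it raises testing. As things stand, a nominally significant result could reflect no more than good and bad recruiting days.

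**Working it through.** **Inputs.** From 2.5.f: 40 days (20 per arm, from the equal allocation in 2.5.a), 100 men per day, 2,000 men per arm, control uptake 8%, ICC 0.02, target difference 5 points (8% against 13%). Assumed: two-sided alpha of 0.05, since the plan gives none.

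**Design effect.** 1 + (100 − 1) × 0.02 = 2.98. Effective sample size per arm = 2,000 / 2.98 = 671.

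**The plan's own power figure.** With 671 per arm, 8% against 13%, pooled variance under the null (mean 10.5%):

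- z = [0.05 − 1.96 × √(2 × 0.105 × 0.895 / 671)] / √[(0.08 × 0.92 + 0.13 × 0.87) / 671] = (0.0500 − 0.0328) / 0.0167 ≈ 1.03, so power is 84.9%.
- With a t reference on 38 df, 83.2%; with a continuity correction, 82.7%; with both, about 81%.
- With 2,000 independent men per arm, 99.9%.

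So the stated 80% is reproduced only when clustering is included.

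**False-positive rate of the unadjusted test.** The true variance of the arm difference is 2.98 times what the test assumes, so the rate is 2 × [1 − Φ(1.96 / √2.98)] = 2 × [1 − Φ(1.135)] = 25.6%. In 100,000 simulated null trials (beta-binomial, 8% uptake, 20 days of 100 men per arm) the plain test rejected in 25.6%, or 24.3% with Yates' correction. A t-test on the 40 day-level proportions rejected in 5.0%.

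**Sensitivity to the ICC**, all of it between days:

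| ICC | Design effect | Actual type I error |
|---|---|---|
| 0.005 | 1.495 | 10.9% |
| 0.01 | 1.99 | 16.5% |
| 0.02 (plan) | 2.98 | 25.6% |
| 0.03 | 3.97 | 32.5% |

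**Sensitivity to stratification.** A stable location effect cancels between arms. If a share s of the ICC of 0.02 is between locations, the variance ratio is 0.98 + 2(1 − s):

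| s | Variance ratio | Actual type I error |
|---|---|---|
| 0 | 2.98 | 25.6% |
| 0.25 | 2.48 | 21.3% |
| 0.5 | 1.98 | 16.4% |
| 0.75 | 1.48 | 10.7% |
| 1 | 0.98 | 4.8% |

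**Logistic model.** With location adjustment, no day term and all correlation between days, simulated rejection was 25.5% (2,000 null trials).

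**What this means in percentage points.** At 8% uptake the naive standard error is √(2 × 0.08 × 0.92 / 2,000) = 0.86 points. The plain test is therefore significant from 1.96 × 0.86 ≈ 1.7 points. Multiplying by √2.98 = 1.726, the threshold should be about 2.9 points, or 3.0 with the t value on 38 df. At 8% against 13% the naive 95% half-width is 1.96 × √[(0.0736 + 0.1131) / 2,000] = 1.9 points; allowing for clustering it is 1.9 × 1.726 ≈ 3.3 points.

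**Power after correction.** The day-level t-test has about 83% power at 8% against 13% (83.5% in simulation) if the ICC is 0.02 in both arms. If instead the between-day coefficient of variation were the same in both arms (k² = 0.02 × 0.92 / 0.08 = 0.23, k = 0.48), day-to-day variance would be larger at 13% and power about 75%.

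**The case against.** The strongest reply is that 25% is the top of a range. It needs a two-sided 5% alpha, an ICC of exactly 0.02, and all of that ICC arising between days within a location. The plan does not say how 0.02 was obtained or how it divides between days and sites. Because allocation is balanced within location, part of it may cancel. At ICC 0.01 with half between locations, the variance ratio is 0.99 + 0.5 = 1.49 and the error rate about 11%. This is fair, and the range belongs beside the headline figure. But the plan defines its cluster as the clinic day, so 25% is the direct reading of its own numbers. The error returns to 5% only if days at the same site do not differ at all.

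Three narrower points also have some force:

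- The plan never says that men are independent. That follows from naming a plain chi-squared test. If an adjusted version was intended, the text must say so.
- The 25.5% for the logistic model comes from adjusting for location only, in a setting with no location variance to remove. Distributor terms might absorb some day-to-day variation if recruiters differ between days. The missing day term is certain; the size of its effect in the full planned model is not.
- HIV positivity is measured among men tested, about 8 to 13 per day at the planning rates. If the same ICC applied, the design effect would be only 1.14 to 1.24 and the error rate about 7 to 8%.

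None of these supplies the missing adjustment for the primary outcome.

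**Conclusion.** The concern holds and must be fixed before analysis. The primary analysis does not match the randomisation, and on the plan's own ICC and cluster size the unadjusted test has about five times its nominal error rate (25.6 / 5 ≈ 5). The figure assumes a two-sided 5% level and correlation that is wholly between clinic days. Over location shares of up to three quarters at ICC 0.02 it runs from about 26% down to 11%. The fault is confined to the analysis: the number of clinic days was chosen with clustering in mind and, at a constant ICC of 0.02, remains enough for a correct test. A lesser point is that a chi-squared test yields a p-value and not the effect estimate that both sections promise. The logistic model would give an odds ratio, but no risk difference or confidence interval is specified.

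**What to change.** Replace the chi-squared test in 2.5.g and in the synopsis Analysis row with one pre-specified analysis at the unit of randomisation. Two suitable choices are:

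- a linear regression (or t-test) on the 40 clinic-day uptake proportions, with location as a fixed effect. With four locations this leaves 40 − 4 − 1 = 35 residual df instead of 38;
- a mixed or GEE model on individual men, with clinic day as the cluster, location fixed effects and a small-sample correction suited to 40 clusters.

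Name the risk difference with a cluster-adjusted 95% confidence interval as the effect measure, and state the significance level and whether the test is two-sided. Carry clinic-day clustering into the logistic and HIV-positivity models as well, noting that its effect on positivity is likely to be small.

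No new data are needed. Cards carry a unique code and distribution date, delivery is logged separately, and the van is at one site per day, so the date identifies both cluster and location. The cost is a wording amendment and wider, but correct, intervals.

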**[Short title: U=U]**

Protocol Version: 1.0  
Version Date: October 31, 2019  
NCT04364165

Study Sponsors  
Bill and Melinda Gates Foundation

Question:	Can messaging about being undetectable equals untransmittable (U=U) increase HIV testing uptake in men?
Purpose:	HIV testing is the gateway to HIV prevention, treatment and HIV control, but uptake is suboptimal in South African men. Consequently, men have poor HIV outcomes including lower HIV testing uptake, lower ART initiation and a lower proportion achieving viral suppression. This study will investigate the effect of participatory, user-designed messaging to increase knowledge about U=U on HIV testing uptake in men in the Klipfontein Mitchells Plain (KMP) district in Cape Town, through a randomized trial design.
Primary objectives:	
1) To develop U=U messaging that encourages HIV testing uptake in men using a participatory, user-centered design. Messaging will seek to assuage the fears of testing HIV positive by conveying the message that HIV treatment makes it possible for HIV positive people to be untransmittable and to live normal lives.
 
2) To investigate the effect of U=U messaging on HIV testing uptake in men compared with the standard of care messaging.

Design:	
The study will be conducted in two phases:
 
Phase 1 is a participatory, human-centered design framework that will be used to develop U=U messages to increase HIV testing uptake in men.
 
Phase 2 is a cluster randomized trial that will determine the effect of U=U messaging on HIV testing uptake. Men in the intervention group will receive invitation cards for mobile HIV testing that contain U=U messages. Men in the control group will receive invitation cards for mobile HIV testing that contain standard messaging. Mobile clinic days (i.e. clusters of men receiving invitation cards at one site on one day) will be the unit of randomization.
 
The primary outcome will be HIV testing uptake at a community-based mobile clinic. Secondary outcomes will include the proportion of males tested who are HIV-positive and newly HIV positive.

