## 2. Methods

**2.1. Objectives** – HIV testing is the gateway to HIV prevention, treatment and HIV control, but uptake is suboptimal in South African men. Consequently, men have poor HIV outcomes including lower HIV testing uptake, lower ART initiation and a lower proportion achieving viral suppression. This study will investigate the effect of a participatory, user designed message to increase knowledge about U=U on HIV testing uptake in men in the Klipfontein Mitchells Plain (KMP) district in Cape Town, through a randomized trial design. The primary objectives of this study are 1) to develop a U=U message that encourages HIV testing uptake in men using a participatory, user-centered workshop, and 2) to investigate the effect of U=U messaging on HIV uptake in men. The primary outcome will be HIV testing uptake at a community-based mobile clinic. Secondary outcomes will include the proportion of males tested who are HIV-positive (and newly HIV positive).

**2.2. Study Duration and Setting** – The study will be 12 months in duration including the preparation period, Phase 1, Phase 2 and analysis. The study will take place in KMP, a resource-limited, densely populated, high HIV disease burden area in Cape Town, where the use of health services among men is sub-optimal. The DTHF Tutu Tester offers mobile HIV testing clinic days in various locations in the region, including KMP. Trained recruiters stationed at the Tutu Tester mobile clinic sites distribute invitation cards inviting men to visit the mobile clinic for a voluntary HIV test. The intervention will utilize the Tutu Tester to trial a new messaging intervention. DTHF will build upon their existing activities and relationship with the local community to implement this study in KMP. DTHF will complete all data collection. Penn will not take part in data collection, nor will Penn interact with the subjects.

**2.3 Inclusion criteria and recruitment** – Recruitment will be conducted by trained mobile clinic staff at selected high foot-traffic sites in the KMP community. Men in high HIV disease burden areas in KMP will also be recruited through community outreach activities to participate in the study. Inclusion criteria for the study will be males at least 18 years of age within the vicinity of the mobile Tutu Tester HIV testing van.

The study will consist of two phases:

### 2.4. Phase 1

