2.5.b. Intervention group – Following phase 1, the final U=U messages will be printed on invitation cards to be distributed at mobile testing sites. Messages will seek to assuage the fears of testing HIV positive by conveying the message that HIV treatment makes it possible for HIV positive people to be untransmittable and to live normal lives. Messages will encourage men to come in for HIV testing at the mobile clinic on the same day. A mobile clinic recruiter will deliver the invitation and share a brief script explaining U=U.

2.5.c. Control group – The standard invitation cards used at the Tutu Tester contain basic information encouraging HIV testing. Messages will encourage men to come in for HIV testing at the mobile clinic on the same day. A mobile clinic recruiter will deliver the invitation and share a brief script including the standard Tutu Tester message.

2.5.d. Study Instruments: Invitation cards – After mobile clinic recruiters deliver the invitation card and scripted verbal message, they will request the participant bring the card with them if they return to test. The card will contain the distribution date and time and recruiter information. The recruiter will also separately record the date and time the invitation was delivered, and whether the mobile clinic was visible on the card. When the participant returns to visit the mobile clinic, the recruiter will request the card and record the date and time of presentation as well as the unique identification code on the card. The participant will then be invited by a counsellor into a cubicle in the mobile clinic to complete a rapid HIV test after the counsellor consents the participant.

2.5.e. Study Instruments: Questionnaire – Key information will be collected from participants who come for testing via tablet. This intake will be completed immediately after an individual arrives at the Tutu Tester and presents their card. This will include a confirmation of inclusion criteria to ensure that the men are at least 18 years old. Other key information will include: type of message (intervention or control), line of sight, date and time of message delivery, date and time of presentation for HIV testing,

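### HIV positivity is compared between arms only among men who tested, so it cannot by itself show whether the U=U message finds more HIV-positive men; add HIV-positive men per card delivered and label positivity descriptive.

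*Combined protocol and SAP*

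**What the plan says.** The synopsis (Design) states: "Secondary outcomes will include the proportion of males tested who are HIV-positive and newly HIV positive". Section 2.1 repeats this, "Secondary outcomes will include the proportion of males tested who are HIV-positive (and newly HIV positive"), and section 2.5.g lists the same proportions as additional outcomes, "Additional outcomes examined will include the proportion of males tested who are HIV-positive (and newly HIV positive"). The denominator is men tested in all three places. The synopsis (Analysis) adds the between-arm contrast: "We will also compare HIV positivity by study arm". No test, model, interval or allowance for clustering is attached to it, and it is not labelled descriptive. Nowhere does the plan define HIV-positive men per card delivered, per man invited or per clinic day.

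The data for such a measure are already planned. Section 2.5.a says "Invitation cards will have unique identification codes". Section 2.5.d says "The recruiter will also separately record the date and time the invitation was delivered". Section 2.5.e puts the decision to stay for a test, and HIV status, on the tablet intake. The intake items listed there include none on previously known HIV status or earlier testing.

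**The concern.** Clinic days are randomised (section 2.5.a). Whether a man tests comes later and is exactly what the message is meant to change. Restricting the comparison to men who tested therefore sets two differently selected groups side by side. Who tests under each message is a fair descriptive question, but the answer is not a randomised effect on the number of positive men found.

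Selection by likely HIV status is plausible here. Section 2.5.b says "Messages will seek to assuage the fears of testing HIV positive", so the extra testers might be positive more often than control testers. They might equally be men at lower risk, and the documents do not settle which. Positivity can fall, stay level or rise while more positive men are found. It is the only HIV-status comparison planned, so a reader could take equal or lower positivity in the U=U arm to mean that the message does not help find infection.

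**Working it through.** **Inputs from the plan.** Section 2.5.f gives 40 clinic days, 100 cards per day, 8% control uptake, an intraclass correlation (ICC) of 0.02 for uptake, and 80% power for a 5-point difference. Section 2.5.a splits days equally within location, so there are about 20 days and 2,000 cards per arm. The planned U=U uptake is 8% + 5 points = 13%.

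**Assumptions.** The documents give no positivity among testers and no ICC for positives per card. Both are assumed below and shown as ranges. They state no significance level either; two-sided 5% is assumed.

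**Plan's own figure.** The design effect is 1 + 99 × 0.02 = 2.98, so the effective size per arm is 2,000 / 2.98 = 671. A t-test with 38 df then has about 83% power for 8% versus 13%. A continuity-corrected calculation needs 629 men per arm: 629 × 2.98 / 100 = 18.7 clusters, plus one for small numbers = 19.7, or 20 days per arm. The stated 80% is reproduced.

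**Men tested.** 0.08 × 2,000 = 160 and 0.13 × 2,000 = 260.

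**General relation.** Let R be the ratio of positivity among tested men, U=U over control. Positives found then have the ratio (260 / 160) × R = 1.625R. They rise if R exceeds 8/13 = 0.615 and fall if R is below it. The two measures disagree in sign when R lies between 0.615 and 1.

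**Illustration.** Assume that the message only adds testers, that it deters no one, and that the other 160 U=U testers are positive at the control rate. Let the 100 extra testers be positive at f times that rate. The positivity ratio is (160 + 100f) / 260 and the positives-found ratio is (160 + 100f) / 160.

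| f | Positivity ratio | Positives-found ratio |
|---|---|---|
| 0.5 | 0.81 | 1.31 |
| 1 | 1.00 | 1.63 |
| 1.25 | 1.10 | 1.78 |
| 1.5 | 1.19 | 1.94 |

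Within this model the signs differ only for f between 0 and 1; above 1 both measures rise.

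**Precision per card, at 10% positivity in both arms.** Expected positives are 16 versus 26, or 8.0 versus 13.0 per 1,000 cards, a difference of 5.0.

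- No clustering: SE = √[(0.008 × 0.992 + 0.013 × 0.987) / 2,000] = 0.00322; 95% CI -1.3 to 11.3 per 1,000; power 34%.
- Only uptake varies by day: the implied ICC is 0.1 × 0.02 × 0.92 / 0.992 = 0.00185 (control) and 0.1 × 0.02 × 0.87 / 0.987 = 0.00176 (U=U). Design effects are 1.18 and 1.17; SE 0.00350; 95% CI -1.9 to 11.9; power about 30%.
- Pessimistic ICC of 0.02: SE = 0.00322 × √2.98 = 0.00556; 95% CI -5.9 to 15.9; power about 14%.

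Over 2% to 20% positivity, power runs from about 10% to 60%, 10% to 47% and 6% to 25% in the three cases.

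**Does a simple interval work with so few events?** In 20,000 simulated trials per case at 10% positivity (20 days per arm, location strata ignored), a 95% t-interval on clinic-day summaries covered the true difference about 95% of the time in all three cases. This held although 45% of control days and 27% of U=U days had no positive man without clustering (64% and 49% at ICC 0.02).

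**The case against.** The best defence is that the plan never calls positivity an effect. Effect language is kept for uptake. Positivity is only compared or examined as an additional outcome, no objective concerns the number of positive men found, and the recommendation in section 5 rests on testing. All of this is true. A reader might infer that the plan misreports a selected comparison as a treatment effect, or that its conclusion is compromised; the documents support neither. What remains is an unlabelled arm comparison that is easy to misread, with no measure of positives found beside it.

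A second argument is that uptake times positivity already gives positives per card. It gives the point estimate, but no planned output gives an interval that allows for clustering.

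Third, the per-card measure would rarely settle the question: at 10% positivity all three intervals above include zero. That stands, and it is why an estimate is requested and not a powered test.

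Fourth, the per-card contrast is not free of selection. Cards are handed out after the day is assigned, and section 2.5.a says "The information content on the referral cards and the mobilization approach will vary depending on condition". Age is confirmed only at presentation, so the denominator may include men under 18. The primary uptake outcome shares these limits. Counting per card removes only the further conditioning on having tested.

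Finally, newly HIV-positive men cannot be assumed countable. The intake list in section 2.5.e may not be exhaustive, but it shows no item on prior status. This objection is accepted and shapes the fix.

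**Conclusion.** The point holds for the secondary HIV outcomes only. As planned, the arm comparison of positivity describes who tests; it can be equal, or reversed in sign, while the U=U message finds more positive men. At the planned uptake, equal positivity corresponds to 1.63 times as many positives found, whatever the positivity level. The f-based ratios rest on the assumption that the message only adds testers; the 8/13 threshold does not.

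A reader might go further and expect the planned comparison to point the wrong way. The documents do not support that: they give no positivity figures, and a message meant to ease fear makes a higher rate among extra testers as arguable as a lower one. Nor is it established that positives found must rise, since they fall if the positivity ratio is below 0.615. The change is worth making because it is cheap, but it is not critical to the trial.

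**What to change.** In section 2.5.g and the synopsis:

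1. Add HIV-positive men per card delivered, by randomised arm, as an estimate with a 95% interval that allows for clinic-day clustering, for example a t-interval on clinic-day summaries with about 20 days per arm. State that it is not a powered test.
2. Keep positivity among tested men and label it descriptive.
3. Report cards delivered per clinic day by arm, and state that the per-card contrast shares the limits of the uptake outcome.
4. Add newly HIV-positive men per card only if that term is defined and an item on prior HIV status is collected. The definition and data source are needed with either denominator.

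For HIV-positive men the cost is wording and one table, because cards, deliveries and HIV status are already recorded. Newly positive men may need an extra intake item. The drawbacks are small counts and wide intervals. Equal card counts would also not show that recipients are alike across arms, since little is recorded on men who do not present beyond delivery time and line of sight.
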